9.1.5. Selection of subjects (including selection of control group if necessary)

Subjects who meet the eligibility criteria and sign the informed consent form will participate in this study. Subjects who do not meet all inclusion criteria or meet any one of the exclusion criteria will not be enrolled to participate in the clinical study.

9.1.5.1. Inclusion criteria

Prospective subjects must meet all of following inclusion criteria to be eligible for implantation:

- Severe aortic stenosis, defined as aortic valve area of <1.0 cm² (or aortic valve area index of <0.6 cm²/m²) by the continuity equation, OR mean gradient >40 mmHg OR maximal aortic valve velocity >4.0 m/sec by resting echocardiogram
- 2. High risk for SAVR defined as STS-PROM score ≥ 8% AND ≤ 15%, OR documented Heart Team agreement of high risk for AVR due to frailty or comorbidities
- 3. Symptoms of aortic stenosis AND NYHA Functional Class II or greater
- 4. The subject and the treating physician agree that the subject will return for all required post procedure follow-up visits

9.1.5.2. Exclusion criteria

Exclusion Criteria

If any of the following exclusion criteria are present, the prospective subject is not eligible for implantation:

- Any condition considered a contraindication for placement of a bioprosthetic valve (e.g., subject is indicated for mechanical prosthetic valve)
- Age is less than 65 years
- A known hypersensitivity or contraindication to any of the following which cannot be adequately pre-medicated:
 - aspirin or heparin (HIT/HITTS) and bivalirudin
 - ticlopidine and clopidogrel
 - nitinol (titanium or nickel)
 - contrast media

MDT18065EVR009 Version 5.0 06-Oct-2023 Page 29 of 121 Medtronic

- Blood dyscrasias as defined: leukopenia (WBC <1000 mm³), thrombocytopenia (platelet count <50,000 cells/mm³), history of bleeding diathesis or coagulopathy, or hypercoagulable states
- Untreated clinically significant coronary artery disease requiring revascularization
- Severe left ventricular dysfunction with left ventricular ejection fraction (LVEF) <20% by echocardiography, contrast ventriculography, or radionuclide ventriculography
- End stage renal disease requiring chronic dialysis or creatinine clearance <20 cc/min.
- Ongoing sepsis, including active endocarditis
- Any percutaneous coronary or peripheral interventional procedure with a bare metal or drug eluting stent performed within 30 days prior to study procedure
- Symptomatic carotid or vertebral artery disease or successful treatment of carotid stenosis within 10 weeks of written informed consent signed
- Cardiogenic shock manifested by low cardiac output, vasopressor dependence, or mechanical hemodynamic support
- Recent (within 6 months of Heart Team assessment) cerebrovascular accident (CVA) or transient ischemic attack (TIA)
- Gastrointestinal (GI) bleeding that would preclude anticoagulation
- Subject refuses a blood transfusion
- Severe dementia (resulting in either inability to provide informed consent for the study/procedure, prevents independent lifestyle outside of a chronic care facility, or will fundamentally complicate rehabilitation from the procedure or compliance with follow-up visits)
- Estimated life expectancy of less than 12 months due to associated non-cardiac co-morbid conditions
- Other medical, social, or psychological conditions that in the opinion of the investigator precludes the subject from appropriate consent or adherence to the protocol required follow-up exams
- Currently participating in an investigational drug or another device study (excluding registries)
- Evidence of an acute myocardial infarction ≤30 days before the study procedure
- Need for emergency surgery for any reason
- Liver failure (Child-Pugh class C)
- Patients requiring TAV implantation via carotid aortic access
- Currently undergoing radiation therapy

Anatomical exclusion criteria:

- Pre-existing prosthetic heart valve in any position
- Mixed aortic valve disease (aortic stenosis with severe aortic regurgitation with predominant aortic regurgitation > 3+)
- Severe mitral regurgitation
- Severe tricuspid regurgitation
- Moderate or severe mitral stenosis
- Hypertrophic obstructive cardiomyopathy
- Echocardiographic or Multi-Detector Computed Tomography (MDCT) evidence of intracardiac mass, thrombus, or vegetation

MDT18065EVR009 Version 5.0 06-Oct-2023 Page 30 of 121 Medtronic

- Non-calcified aortic valve
- Unicuspid valve verified by echocardiography
- Bicuspid aortic valve with no raphe or 2 raphes (Sievers classification type 0 or type 2)
- Sinus of Valsalva diameter unsuitable for placement of the self-expanding bioprosthesis
- Aortic annulus diameter of < 18 or > 26 mm.
- Significant ascending aortopathy requiring surgical repair
- Ascending aorta diameter > 4.5 cm
- For transfemoral access vessel diameter < 5.5 mm or for transaxillary (subclavian) access < 6.0
 mm in patients with a patent left internal mammary artery (LIMA)

9.1.5.3. Criteria and procedures for trial/treatment termination

The study enrollment was completed in February 2023, all the enrolled subjects will continue to be followed up for 5 years post procedure.

9.1.5.4. Time of enrollment

If the patient agrees to participate, written informed consent will be obtained. The date of the ERC confirms the subject is eligible will be considered the point of enrollment.

The study enrollment was completed in February 2023.

9.1.5.5. Estimated duration of clinical trial and the reasons for determination

Subjects will be consented for follow-up through 5 years. The enrollment phase of the study was completed; the estimated total duration of the study (first subject enrolled to last subject completing his/her last follow-up visit) is estimated to be 6.5 years, excluding the time required for preparing the study start-up, final report and study closure.

9.1.5.6. Estimated participation duration of each subject

Each implanted subject whether in the roll-in or primary study population will be followed up to 5 years post-procedure. Subjects who are taken to the procedure room for implantation but do not receive an Evolut PRO for any reason will be exited from the study within 30-days post the date of implant procedure unless a study system and/or implant procedure related Adverse Event (AE) is identified. If a study system and/or implant procedure related AE is identified, the subject will be followed until the event is resolved or no further actions need to be taken.

In the rare event the Evolut PRO TAV is explanted from the subject, their participation in the study ends following discharge from the explant hospitalization or 30 days post-explant (whichever comes later) to assess safety and then terminated from the study.

MDT18065EVR009 Version 5.006-Oct-2023

Page 31 of 121

Medtronic

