10.1. Statistical design, method and analysis procedures

This is a prospective, single arm, multi-center, interventional, post-market study. The primary endpoints are all-cause mortality and the percentage of evaluable echocardiograms with moderate or severe prosthetic aortic valve regurgitation at 30 Days. As this is not a powered hypothesis-driven study, the sample size was not determined by statistical methods. The sample size is consistent with the 50 subject minimum as outlined NMPA TAVI Clinical Trial Guideline²⁹.

Subjects who are taken to the procedure room and attempt the implantation will comprise the study population evaluated for the study objectives and associated endpoints. Data from subjects enrolled as roll-ins will not be combined with the primary analysis cohort and will be analyzed separately. The analysis subsets for the study endpoints are shown in Figure 5.

[figure not shown]

Figure 5. Analysis sets for the study endpoints

There are 2 main analysis sets for the primary study population:

- 1. **Attempted implant set.** Includes all subjects who are brought into the procedure room and any of the following have occurred: anesthesia administered, vascular line placed, TEE placed, or any monitoring line placed.
- 2. **Implanted set.** Includes all subjects who are implanted with the Evolut PRO, defined as the Evolut PRO is placed in the aortic annulus and completely released from the delivery catheter system.

Statistical analysis of primary and secondary endpoints was performed when the primary study population (n= 50 subjects with attempted implant, exclusive of "roll-in" patients) were followed for 30 days. Results for the baseline characteristics and the primary and secondary endpoints from the 60-subject TAVR 2.0 US Clinical Study (Evolut PRO) will be provided for descriptive comparison. In addition, results will be descriptively compared to available results for other commercially approved TAVR systems in China.

Data will be analyzed and Clinical Study Reports (CSRs) will be prepared for the primary endpoint (at 30 days) and for the final analysis. The final analysis will be performed when all implanted subjects have completed their 5-year follow-up. Annual CSRs may also be prepared after the primary endpoint and prior to the final analysis CSRs, per the discretion of the Sponsor.

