#### 5. **Investigation Plan**

This is a prospective, single arm, multi-center, interventional, post-market study. Subjects will be consented for follow-up through 5 years. The enrollment phase of the study was completed; the estimated total duration of the study (first subject enrolled to last subject completing his/her last followup visit) is estimated to be 6.5 years, excluding the time required for preparing the study start-up, final report and study closure.

The study will be conducted at approximately 6 centers with a maximum of 8 centers in China with approximately 65 subjects with a maximum of up to 70 subjects with an attempted implant using the Evolut PRO system. There is no minimum number of subjects required for each clinical institution. No site will implant more than 20 subjects, excluding the roll-in subjects, without prior authorization from Medtronic. By completion of the enrollment phase, 58 attempted implanted subjects from 4 activated sites were enrolled.

Subjects who are taken to the procedure room for implantation but do not receive an Evolut PRO for any reason will be exited from the study within 30-days post the date of implant procedure unless a study system and/or implant procedure related Adverse Event (AE) is identified. If a study system and/or implant procedure related AE is identified, the subject will be followed until the event is resolved or no further actions need to be taken. In the rare event the Evolut PRO TAV is explanted from the subject, their participation in the study ends following discharge from the explant hospitalization or 30 days post-explant, or through resolution of potential related adverse events (whichever comes later) to assess safety and then terminated from the study.

Estimating 65 subjects with a maximum of up to 70 subjects in China with an attempted implant, comprised of the following:

- 1) Primary study population: 50 subjects with an attempted implant using the Evolut PRO system
- 2) Roll-in population: The first two attempted subjects at each site will be considered "roll-in" subjects. The maximum number of roll-in subjects among all sites will be 20 subjects. The roll-in population will be followed per the same protocol as the primary study population; however, results from the roll-in population will be analyzed separately from the primary study population.

[figure not shown]

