The primary analysis for the primary safety objective, secondary safety objectives, device success, and the additional outcome measures of safety outcomes, NYHA and quality of life will use the attempted implant set. Primary efficacy endpoint, valve performance, and other outcome measures related to valve dysfunction, and hemodynamic performance metrics will use the implanted set.

Revision 3.0

Page 14 of 23

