#### **Sensitivity Analysis:**

Sensitivity analysis will be performed using the following criteria. Proportions and 95% confidence intervals under each scenario will be reported:

- Complete analysis: excludes all subjects that dropped out or withdrew before 30 days
- Worst-case analysis: assumes all subjects that dropped out or withdrew before 30 days are dead
- Best-case analysis: assumes all subjects that dropped out or withdrew before 30 days are alive
- Tipping point analysis: if the number of missing subjects is n (n>1), a stepwise analysis between the best-case and worst-case scenarios will be conducted by the following steps:
  - Step 1: assumes one subject is dead, n-1 subjects alive, and calculate the proportion.
  - Step 2: assumes two subjects are dead, n-2 subjects alive, and calculate the proportion.

The calculation will be iterative until the last step: assumes n-1 subjects are dead, one subject alive, and calculate the proportion.

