#### 2. All-cause mortality at 6 months, one year, and annually through 5 years

Event rate estimates will be provided at 6 months, 1 year and annually through 5 years for the attempted implant set. The outcome is descriptive including Kaplan-Meier rates and no statistical hypothesis test is specified.

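### Five-year mortality and stroke are estimated on all attempted implants, but explanted and never-implanted subjects leave follow-up early, so their later deaths and strokes are not collected

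*Protocol*

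**What the plan says.** **Who is analysed.** SAP 7.1.3 states that the "additional outcome measures of safety outcomes, NYHA and quality of life will use the attempted implant set". Membership requires entry to the procedure room plus any one of "anesthesia administered, vascular line placed, TEE placed, or any monitoring line placed" (CIP 10.1); a valve need not be implanted. For all-cause mortality, SAP 7.10.5 item 2 says "Event rate estimates will be provided at 6 months, 1 year and annually through 5 years for the attempted implant set", using Kaplan-Meier. The item on all stroke is set up in the same way.

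**Who is followed.** CIP 9.1.5.6 says "Each implanted subject whether in the roll-in or primary study population will be followed up to 5 years post-procedure", and then makes two exceptions:
- Subjects who are taken to the procedure room but "do not receive an Evolut PRO for any reason will be exited from the study within 30-days post the date of implant procedure". A system- or procedure-related adverse event keeps them in only until it resolves or nothing more can be done.
- After an explant, "their participation in the study ends following discharge from the explant hospitalization or 30 days post-explant (whichever comes later").

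CIP 9.2.5 repeats both exits. SAP section 5 repeats them too, but adds to the explant rule "or through resolution of potential related adverse events (whichever comes later"), which the CIP does not contain.

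**What happens after exit.** CIP 9.2.6 refers subjects who leave to routine care and describes no further study data collection. SAP 7.2.2 censors at the latest contact and SAP 7.4 at discontinuation. The final analysis waits only for implanted subjects to reach 5 years (CIP 10.1).

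**Sensitivity analysis.** SAP 7.10.1 has complete-case, best-case, worst-case and tipping-point analyses for 30-day mortality, for example "Worst-case analysis: assumes all subjects that dropped out or withdrew before 30 days are dead". Nothing comparable is planned from 6 months to 5 years.

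**The concern.** The population named in the long-term estimates is wider than the population followed. Subjects leave because the procedure did not end with a study valve, or because the valve was removed. Kaplan-Meier gives a censored subject the later risk of those still under observation, who are nearly all living with the valve in place. Nothing in the documents supports that assumption for someone whose valve was taken out, for example for endocarditis or thrombosis. The censoring is therefore probably informative, and a figure labelled as mortality in all attempted subjects moves towards mortality while the study valve stays in place.

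These estimates are still pending. The last study implant was in February 2023 (CIP 7.2.6), so 5-year follow-up runs to about early 2028. CIP sections 6 and 22 say the data may support new device generations or expanded indications. Vital status that is not recorded becomes harder to recover as time passes.

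**Working it through.** The plan gives no figure of its own to reproduce: it has no hypothesis and no expected 5-year mortality. The one available count reconciles: 50 primary subjects plus 2 roll-ins at each of 4 sites = 58.

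**Input from the documents:** n = 50 attempted implants in the primary population (CIP 10.2.1).

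**Assumptions, because the documents do not give these values:** k = 1 or 3 subjects explanted early and censored alive; D = 15 or 20 deaths among the other 50 − k, all of whom are followed to year 5.

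**Formulas**
- Kaplan-Meier with the k subjects censored early: KM = D/(50 − k).
- Full vital status, with a fraction m of the exited subjects dying: (D + km)/50.
- Difference (full minus KM): (k/50) × (m − KM).

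The last line gives the direction. KM is too low if exited subjects die more often than those still followed (m > KM), too high if they die less often, and correct if the risks are equal or k = 0.

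| k | D | KM | all exited die | understated by | all exited survive | overstated by |
|---|---|---|---|---|---|---|
| 1 | 15 | 15/49 = 30.6% | 16/50 = 32.0% | 1.4 | 15/50 = 30.0% | 0.6 |
| 1 | 20 | 20/49 = 40.8% | 21/50 = 42.0% | 1.2 | 20/50 = 40.0% | 0.8 |
| 3 | 15 | 15/47 = 31.9% | 18/50 = 36.0% | 4.1 | 15/50 = 30.0% | 1.9 |
| 3 | 20 | 20/47 = 42.6% | 23/50 = 46.0% | 3.4 | 20/50 = 40.0% | 2.6 |

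**Later explant.** Assume 40% mortality at 5 years, constant hazard, and explant at year 2. Mortality from year 2 to year 5 among those still followed is 1 − 0.6^(3/5) = 26.4%. If all k die, the shortfall is (k/50) × (1 − 0.264): 1.5 points for k = 1 and 4.4 for k = 3. If all survive, the excess is (k/50) × 0.264: 0.5 and 1.6 points. Timing changes the size little.

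**Against sampling error.** The approximate 95% half-width is 1.96 × √(p(1 − p)/50), which is 12.7 points at p = 0.30 and 13.6 at p = 0.40.

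**30 days.** A never-implanted subject can exit before the visit window of day 30 to 45. Each such subject who then died by day 30 would be worth 1/50 = 2.0 points.

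**Stroke.** The same reasoning applies. No stroke figure is offered, because that analysis also censors at death (SAP 7.2.2) and the simple formula no longer holds.

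**The case against.** The strongest reply is that the affected group may be empty. The CIP calls explant rare, and the documents report neither explants nor failed implants. The outcomes concerned are descriptive, listed under other outcome measures, with no pass/fail criterion, and even the worst case lies well inside the confidence interval. All of this stands, and it limits the size of the point. It does not supply the missing data: unlike sampling error, a systematic gap is not shown by the interval.

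A reader might also draw four stronger conclusions, which the documents do not support.
- *That deaths after device failure go uncounted.* Deaths up to discharge or 30 days post-explant are counted, as are deaths with a failed valve in place and deaths while a never-implanted subject is kept in for a related adverse event. Failure managed without explant, such as balloon dilatation or a second valve inside the first, triggers no exit. Only events after the rule-driven exit are lost.
- *That the estimate is necessarily biased in the device's favour.* Kaplan-Meier does not treat exited subjects as survivors, and the table shows that the error can go either way. A favourable direction is probable, not established.
- *That the 30-day primary result is compromised.* That analysis was completed under CIP 4.0 (CIP 10.1.1). SAP 7.5.2 records no reintervention before the 30-day visit, and the CIP definition of reintervention includes surgical replacement. Only an early exit of a never-implanted subject could matter there. SAP 7.10.1 refers to drop-outs and withdrawals, which leaves open whether mandated exits are included; but CIP 9.2.6 treats explants as discontinuations, and the tipping-point step counts missing subjects without regard to reason.
- *That extended contact is already covered by consent.* CIP 9.1.5.5 speaks of consent to 5 years, but 9.1.5.6 ends participation at explant, and the consent form is a separate document.

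**Conclusion.** The point holds for mortality and stroke after 30 days. The analysis set, the exit rules and the censoring rule together mean that events after a rule-driven exit are not collected, and no planned analysis shows what that could do to the result. With 1 to 3 early explants among 50 and 15 to 20 other deaths, 5-year mortality would be understated by about 1.2 to 4.1 points if every exited subject dies and overstated by about 0.6 to 2.6 points if all survive. Both ends are bounds under assumed counts; with no exits the effect is zero. This is a cheap improvement to a pending estimate and does not invalidate the study. Separately, the CIP and SAP explant exit rules differ, so censoring dates could depend on which document is followed.

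**What to change.** - **CIP 9.1.5.6 and 9.2.5, SAP 5:** end device and echo assessments at exit, but collect vital status and stroke by telephone or records at each annual window to year 5 for all attempted subjects. Obtain ethics committee agreement or re-consent where needed, including for anyone already exited.
- **SAP 7.10.5:** report the number of rule-driven exits, separately for explanted and never-implanted subjects, and add best- and worst-case bounds for mortality and stroke at the later time points.
- **If follow-up cannot be extended:** label these estimates as follow-up while the study valve is in place, and still report the exits and the bounds.
- **30-day result:** check whether any attempted subject exited before day 30, and state the answer in a footnote.
- **Explant exit rule:** reconcile the CIP and SAP wording.

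The cost is a minor amendment and a yearly contact for a few subjects at most, plus records for event adjudication where an event occurs. No added clinic visits or tests are needed; CIP Table 3 already accepts telephone or email at 6 months. The reported mortality may turn out slightly less favourable.

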9.1.5.7. Number of subjects required for clinical trial

The study was designed estimating 65 subjects with a maximum of up to 70 subjects in China with an attempted implant. At the completion of enrollment, 58 subjects in China with an attempted implant were enrolled, comprised of the following:

- 1) Primary study population: 50 subjects with an attempted implant using the Evolut PRO system
- 2) **Roll-in population**: The first two attempted subjects at each site were considered "roll-in" subjects. The maximum number of roll-in subjects among all sites was 20 subjects. At completion of enrollment, there were 8 total roll-in subjects enrolled. The roll-in population will be followed per the same protocol as the primary study population; however, results from the roll-in population will be analyzed separately from the primary study population.

9.1.6. Efficacy evaluation method

The primary and secondary efficacy endpoints were evaluated by quantitative assessment of transthoracic echocardiograms (TTE) by an independent Echo Core Laboratory and determination of the device success composite endpoint per the Valve Academic Research Consortium-2 (VARC II) definition¹. As the study has transitioned post-market, all other endpoints will be evaluated via quantitative assessment of TTE by each site.

